8.1.1. Study Completion and End of Trial

Part A and Part B of this study will be considered complete (that is, the scientific evaluation will be complete [study completion]) approximately 6 months after the last patient in Part B of the study has been enrolled, and Part C of this study will be considered complete approximately after all the patients in Part C have completed 8 cycles or discontinued early. Investigators will continue to follow the study schedule for all patients until notified by Lilly that study completion has occurred. “End of trial” refers to the date of the last visit or last scheduled procedure for the last patient.

The end of trial occurs after study completion and after the last patient has discontinued study treatment and completed any applicable continued access follow-up.

^a Lilly will notify sites when continued access period begins and ends.

^b Part A and Part B of this study will be considered complete approximately 6 months after the last patient in Part B has been enrolled, and Part C of this study will be considered complete approximately after all the patients in Part C have completed 8 cycles or discontinued early.

Figure JFCQ.8.2. Study period and continued access diagram.

8.1.2. Continued Access Period

The continued access period will apply to this study only if at least 1 patient is still on study treatment when study completion occurs. Patients receiving study treatment and experiencing ongoing clinical benefit and no undue risks may continue to receive study treatment in the continued access period until one of the criteria for discontinuation is met (Section 7.3). Lilly will notify investigators when the continued access period begins.

Patients who are in short-term follow-up when the continued access period begins will continue in short-term follow-up until the 30-day short-term follow-up visit is completed. Long-term follow-up does not apply.

Patients who are in long-term follow-up when the continued access period begins will be discontinued from long-term follow-up.

During the continued access period, all AEs, SAEs, and study drug exposure will be reported on the CRF. Serious adverse events will also be reported to Lilly Global Patient Safety (see Section 10.2.1). In the event that an SAE occurs, Lilly may request additional information (such as local laboratory results, concomitant medications, and hospitalizations) in order to evaluate the reported SAE. Blood samples for PK and immunogenicity analysis for necitumumab will be collected in the event of an IRR and during the continued access follow-up.

During the continued access period, the sponsor will collect only the data shown in [Attachment 1](#). It is recommended that routine monitoring, using an assessment schedule similar to that outlined in [Attachment 1](#) (including radiographic evaluation of disease), be continued as necessary to confirm patient eligibility to continue on treatment. However, the results of all these assessments may not be routinely collected by the sponsor, and all nonmandatory assessments (that is, all assessments not explicitly described in [Attachment 1](#)) may be performed locally rather than centrally.

8.2. Discussion of Design and Control

In this open-label, Phase 1b study with an expansion cohort, the selected fixed-dose of pembrolizumab of 200 mg on Day 1 Q3W is an experimental dose but the differences in exposure for a 200-mg fixed-dose regimen relative to a 2-mg/kg Q3W body weight-based regimen registered currently for melanoma indication are anticipated to remain well within the established exposure margins for this compound. The starting dose of necitumumab in Part A (patients with Stage IV NSCLC) will be at dose level -1 of the MTD (600 mg on Days 1 and 8 Q3W). Since this is the first time these 2 mAbs are combined in a clinical setting, the recommended, biologically active dose of pembrolizumab was selected and it was chosen to use a DLT-driven design to escalate necitumumab to MTD.

Patients with Stage IV NSCLC who have progressed after 1 platinum-based chemotherapy regimen will receive a combination of necitumumab and pembrolizumab. Prior treatment with EGFR-TKI, VEGF/VEGFR-targeting agents, and ALK inhibitors is permitted.

In Part B, approximately 54 patients with Stage IV NSCLC with an approximately even split between squamous and nonsquamous histology will be enrolled to enable evaluation of safety and efficacy parameters by histology.

Provided there is an acceptable safety profile in Part A of this study, Part B will be initiated, which will include an interim safety analysis after the first 15 evaluable patients have completed 2 cycles of study treatment (or otherwise discontinued study treatment). Patients with squamous and nonsquamous NSCLC from Part A who received the recommended necitumumab dose for Part B will be included in the safety interim analysis.

In Part C, 6-12 Japanese patients with Stage IV NSCLC with squamous and nonsquamous histology will be enrolled to enable evaluation of safety and efficacy parameters using a fixed

200-mg dose of pembrolizumab given Q3W and necitumumab dose as determined in the Part A of the study.

The outcome will be hypothesis generating only, allowing for future consolidation of this regimen depending on the outcome.

9. Treatment

9.1. Treatments Administered

The following treatments will be administered in this study (Table JFCQ.9.1):

In Part A, patients will receive I.V. necitumumab 600 mg or 800 mg on Day 1 and Day 8 Q3W in combination with pembrolizumab 200 mg as an absolute dose on Day 1 Q3W.

In Part B and Part C, the necitumumab dose identified from Part A will be given on Day 1 and Day 8 Q3W in combination with pembrolizumab 200 mg as an absolute dose Day 1 Q3W.

Pembrolizumab will be administered first followed by necitumumab.

Table JFCQ.9.1. Treatment Regimens/Dosing Schedule

Part A

Cohort	Drug	Dose	Day of 21-day Cycle	Infusion Duration
Cohort 1	Pembrolizumab	200 mg absolute dose I.V. infusion	Day 1	Over 30 minutes ^a
	Necitumumab	600 mg dose I.V. infusion	Days 1 and 8	Over 60 minutes ^b
Cohort 2	Pembrolizumab	200 mg absolute dose I.V. infusion	Day 1	Over 30 minutes ^a
	Necitumumab	800 mg dose I.V. infusion	Days 1 and 8	Over 60 minutes ^b

Part B and Part C

Drug	Dose	Day of 21-day Cycle	Infusion Duration
Pembrolizumab	200 mg absolute dose I.V. infusion	Day 1	Over 30 minutes ^a
Necitumumab	Recommended dose from Part A I.V. infusion	Days 1 and 8	Over 60 minutes ^b

Abbreviation: I.V. = intravenously.

^a Sites should make every effort to target infusion timing to be as close to 30 minutes as possible. However, given the variability of infusion pumps from site to site, a window between -5 minutes and +10 minutes is permitted (i.e., infusion time is 30 minutes -5 min/+10 min, i.e., between 25 to 40 minutes).

^b At the time of approval of the JFCQ(c) protocol amendment, all patients who are still on the study will be administered necitumumab I.V. infusion over 60 minutes.

Based on the independent necitumumab and pembrolizumab clinical development programs, the individual recommended doses are 800 mg on Day 1 and Day 8 Q3W for necitumumab and 200 mg on Day 1 for pembrolizumab. For this reason, further dose escalation beyond Cohort 2 will not be tested.

Hypersensitivity/infusion-related reactions (IRRs) may occur during or following administration of necitumumab (see Section 9.4.1.3.1 for a definition of Grade 3 and 4 hypersensitivity/IRRs). As a routine precaution, patients treated with necitumumab should be observed closely for any potential adverse effects by the medical staff from the start of the infusion until at least 1 hour after the end of the infusion in an area with resuscitation equipment and other agents (for example, epinephrine or prednisolone equivalents) available.

The investigator or his/her designee is responsible for the following:

- explaining the correct use of the drugs and planned duration of each individual's treatment to the patient,
- verifying that instructions are followed properly,
- maintaining accurate records of study drug dispensing and collection,
- and returning all unused medication to Lilly or its designee at the end of the study.

Note: In some cases, sites may destroy the material if, during the investigator site selection, the evaluator has verified and documented that the site has appropriate facilities and written procedures to dispose clinical trial materials.

Patients will be instructed to contact the investigator as soon as possible if they have a complaint or problem with the study drug so that the situation can be assessed.

9.2. Materials and Supplies

Necitumumab will be provided by Lilly and pembrolizumab will be provided by Merck (all materials will be packaged and shipped from Lilly, and will bear Lilly clinical trial material labeling). Clinical trial materials will be labeled according to the country's regulatory requirements.

Necitumumab is a sterile and preservative-free solution for I.V. infusion supplied in the following formulation:

- Necitumumab solution for infusion at a final concentration of 16 mg/mL (800 mg/50 mL) contained in single-use vials, in a formulation of 10 mM citrate, 40 mM sodium chloride, 133 mM glycine, 50 mM mannitol, 0.01% polysorbate-80, pH 6.0.

All excipients used in the formulation of necitumumab are of pharmacopeial grade. No animal-derived components are used in the manufacture of necitumumab excipients. The drug product must be stored under refrigeration at 2°C to 8°C with protection from light. Refer to necitumumab IB for detailed storage information.

Pembrolizumab drug product is available in 2 dosage forms: a white to off-white lyophilized powder, 50 mg/vial, and a liquid, 100 mg/vial, both in Type I glass vials intended for single use only.

- Pembrolizumab Powder for Solution for Infusion, 50 mg/vial, is a lyophilized powder that is reconstituted with sterile water for injection prior to use. Pembrolizumab is formulated with L-histidine as buffering agent, polysorbate 80 as surfactant, sucrose as stabilizer/tonicity modifier, and may contain hydrochloric acid and/or sodium hydroxide for pH adjustment (if necessary).
- Pembrolizumab Solution for Infusion 100 mg/vial is a liquid, manufactured fully formulated with L-histidine as a buffering agent, polysorbate 80 as a surfactant, and sucrose as a stabilizer/tonicity modifier.

Both pembrolizumab product dosage forms are stored under refrigerated conditions 2°C to 8°C (36-46°F) and protected from light. Refer to pembrolizumab IB for detailed storage information.

9.3. Method of Assignment to Treatment

An interactive web response system (IWRS) will be utilized for drug dispensing for Parts A, B, and C of the study.

For patients in Part B, enrollment will be balanced to include approximately 50% squamous and 50% nonsquamous patients. Patients will be registered in the IWRS, which consists of assigning a unique study identification number and entering the patient's tumor histology type (squamous vs. nonsquamous). Once the patient is registered in the IWRS, he or she is considered being enrolled in the study. Enrollment into the IWRS will be disabled once enrollment goals have been met for both histology types.

9.4. Selection and Timing of Doses

The first treatment will be administered within 7 days of enrollment. Study treatment will be administered as described in Section 9.1.

A cycle is defined as an interval of 21 days.

Administration of pembrolizumab Day 1 dose, followed by necitumumab will trigger the start of a new cycle. Infusions administered within 3 days before or after the planned infusion time point due to holidays, weekends, bad weather, or other unforeseen circumstances will be permitted and not counted as a protocol deviation. The necitumumab Day 8 dose can be delayed up to 5 days. Beyond that, the Day 8 dose will have to be omitted in order to maintain the 21 day cycle. **A minimum of 7 days' interval between any necitumumab doses must be maintained.**

A patient may continue to receive study treatment until he or she meets 1 or more of the specified reasons for discontinuation (as described in Section 7.3), or complete remission is diagnosed (as described in Section 8.1).

9.4.1. Special Treatment Considerations

9.4.1.1. Dose-Limiting Toxicity (Parts A and C)

A DLT is defined as one of the following AEs, occurring in Cycle 1 if considered to be definitely, probably, or possibly related to necitumumab and pembrolizumab. The following list will define DLT:

- Grade 3 or 4 nonhematologic toxicity according to the NCI-CTCAE Version 4.0, except for skin toxicity, nausea, vomiting, diarrhea, or electrolyte disturbance (see below). For patients with \leq Grade 2 hepatic transaminase levels at baseline as a result of liver metastases, a transaminase level ≥ 10 x ULN lasting for >7 days will be considered a DLT.
- Grade 4 nausea, vomiting, or diarrhea that persists more than 3 days despite maximal supportive intervention
- Grade 3 thrombocytopenia with bleeding requiring transfusion
- Grade 4 thrombocytopenia with or without bleeding
- Grade 4 neutropenia that persists more than 5 days
- Grade 3 or 4 neutropenia with fever, defined as single temperature of $>38.3^{\circ}\text{C}$ (101°F) or a sustained temperature of $\geq 38^{\circ}\text{C}$ (100.4°F) for more than one hour
- Grade ≥ 3 skin toxicity despite best supportive care, with exception of Grade 3 rash that resolves to Grade ≤ 2 within 14 days with appropriate supportive therapy
- If a total at least 75% of the planned dose for both agents cannot be administered in the first cycle due to toxicity
- Prolonged delay (>2 weeks) in initiating cycle 2 due to treatment-related toxicity
- Grade 5 toxicity

DLT is defined by sponsor and principal investigator.

The following toxicities will not be considered DLTs if they are transient (<7 days):

- Hypersensitivity and injection site reactions (If a Grade 3 or 4 hypersensitivity/IRR to necitumumab or pembrolizumab occurs, this event will not be considered a DLT; the patient will not receive any further study therapy and will be replaced in the study by a new patient.)
- Grade ≥ 3 myalgia, fatigue, or constipation, with full supportive therapy
- Grade ≥ 3 increase or decrease of electrolytes
- Grade 3 nausea, vomiting, or diarrhea that resolves to Grade ≤ 1 within 7 days of appropriate supportive therapy
- Grade ≥ 3 elevation of serum creatine kinase level that is asymptomatic that returns to Grade ≤ 2 within 21 days of necitumumab treatment interruption

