interim analysis	An interim analysis is an analysis of clinical trial data, that is conducted before the final reporting database is created/locked.

investigational product (IP) [hereon referred to as study treatment]	
A pharmaceutical form of an active ingredient substance or placebo being tested, or used as a reference, in a clinical trial. Investigational product (IP) includes a product with a marketing authorization when:
 
 1. used or assembled (formulated or packaged) in a way different from the authorized form, 2. used for an unauthorized indication, or 3. used to gain further information about the authorized form. 
In this study, the IPs are necitumumab (LY3012211; IMC-11F8) and pembrolizumab (MK-3475).

investigator	A person responsible for the conduct of the clinical trial at a trial site. If a trial is conducted by a team of individuals at a trial site, the investigator is the responsible leader of the team and may be called the principal investigator.
irCR	immune-related complete response
irPD	immune-related progressive disease
irPR	immune-related partial response
irRECIST	immune-related Response Evaluation Criteria in Solid Tumors
IRR	infusion-related reaction
irSD	immune-related stable disease
I.V.	intravenous(ly)
IWRS	interactive web-response system
legal representative	An individual, judicial, or other body authorized under applicable law to consent on behalf of a prospective patient to the patient's participation in the clinical study.
Lilly Safety System	Global safety database that tracks and reports serious adverse and spontaneous events occurring while using a drug/drug delivery system.
mAb	monoclonal antibody
MedDRA	Medical Dictionary for Regulatory Activities
mOS	median overall survival
mPFS	median progression-free survival
MRI	magnetic resonance imaging
MTD	maximum tolerated dose
NCI-CTCAE	National Cancer Institute Common Terminology Criteria for Adverse Events
NSAIDs	non-steroidal anti-inflammatory drugs

NSCLC	non-small cell lung cancer
ORR	overall response rate
OS	overall survival
patient	A study participant who has the disease or condition for which the investigational product is targeted.
PC	pemetrexed–cisplatin
PC+N	necitumumab plus pemetrexed–cisplatin
PD	progressive disease
PD-1	programmed death-1
PD-L	programmed death-1 ligand
PFS	progression-free survival
PI	package insert
PK	pharmacokinetic(s)
PopPK	population pharmacokinetics
PR	partial response
PT	prothrombin time

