7.3.2. Discontinuation of Study Therapy

Patients will be discontinued from the study treatment in the following circumstances:

- Enrollment in any other clinical trial involving a study drug or enrollment in any other type of medical research judged not to be scientifically or medically compatible with this study.
- The patient, for any reason, requires treatment with another therapeutic agent that has been demonstrated to be effective for treatment of the study indication; discontinuation from study therapy occurs prior to introduction of the new agent.
- Investigator/Physician Decision
 - The investigator/physician decides that the patient should be withdrawn from the study due to an intercurrent illness or change in the patient's condition that renders the patient unsuitable for further treatment in the opinion of the investigator.

- Any study therapy-related event that is deemed life-threatening, regardless of grade, warrants discontinuation of that therapy and/or discontinuation from all therapy if appropriate in the opinion of the investigator.
- If the patient has progressive disease (PD, confirmed by irRECIST or unconfirmed but with clinically worsening/deterioration [Section 10.1.5.1 and Table JFCQ.10.1]).
- Any event(s) which would require a given study therapy to be modified by more than 2 dose reductions or to be held for more than 6 weeks following Day 1 of the most recent cycle warrants discontinuation of that therapy.
- The patient becomes pregnant during treatment.
- Patient Decision
 - The patient or patient's designee (for example, parents or legal guardian) requests to be withdrawn from the study or study treatment.
- Sponsor Decision
 - The sponsor stops the study or stops the patient's participation in the study for medical, safety, regulatory, or other reasons consistent with applicable laws, regulations, and good clinical practices (GCP).
- The patient is significantly noncompliant with study procedures and/or treatment.
- An unacceptable AE/toxicity (for example, a persistent moderate toxicity that is intolerable to the patient).
- A Grade 3 to 4 IRR, and potentially other drug-related AEs, as specified in Section 9.4.1 below.

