A treatment cycle will be defined as 21 days. Study therapy, consisting of necitumumab plus pembrolizumab, will continue until there is a radiographic documentation of PD, toxicity requiring cessation, protocol noncompliance, or withdrawal of consent. Discontinuation of treatment may be considered for patients who have attained a confirmed CR that have been treated for at least 24 weeks from Cycle 1 Day 1 with pembrolizumab and necitumumab or pembrolizumab alone and had at least 2 treatments with pembrolizumab with or without necitumumab beyond the date when the initial CR was declared.

Part C:

Part C will only enroll patients from Japan. It is a single-arm study to evaluate safety and tolerability of necitumumab at the recommended dose identified from Part A of the study on Days 1 and Day 8 Q3W in combination with pembrolizumab 200 mg on Day 1 Q3W in Japanese patients with stage IV NSCLC (Figure JFCQ.8.1).

Part C will first enroll 6 patients. If 2 out of 6 patients experience DLTs, the sponsor will examine the safety data and consult with an external committee as needed. The sponsor will decide if the dose is intolerable, or if additional patients will be enrolled to the same dose level (or lower dose level) for further investigation. If additional patients are needed, 6 additional Japanese patients will be enrolled (to maximum of 12 Japanese patients in Part C).

Terms used to describe the periods during the trial are defined below:

- **Baseline:** begins when the ICF is signed and ends at the first study treatment (or at discontinuation, if no treatment is given).
- **Study Period:** begins at the first study treatment and ends at study completion. The study period does not include the continued access period.
 - **Study Treatment Period:** begins at the first study treatment and ends when the patient and the investigator agree that the patient will no longer continue study treatment. The date of this agreement is to be reported on the case report form (CRF) as the Date of Discontinuation from study treatment.
- **Postdiscontinuation Follow-Up:** begins the day after the patient and the investigator agree that the patient will no longer continue study treatment.

Short-term follow-up begins the day after the patient and the investigator agree that the patient will no longer continue study treatment and lasts approximately 30 days.

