9.4.1.2.2. Necitumumab

Prior to each administration of necitumumab, all toxicities associated with necitumumab must have resolved to Grade ≤ 2 (except for alopecia and skin toxicity) or baseline. Pretreatment laboratory data may not be older than 72 hours (Day 1 of each cycle) or 24 hours (Day 8 of each cycle).

If the criteria are not met at the time of a planned treatment, the following general rules for the management of treatment delays apply:

- In the case of reversible Grade 3-4 necitumumab-related toxicity (for example, fatigue, anorexia, and fever), administration of necitumumab will be at the reduced dose (refer to [Section 9.4.1.2.2.1](#)) or interrupted, but pembrolizumab will continue according to the planned schedule.
- If administration of necitumumab is delayed for more than 6 weeks (2 cycles) after Day 1 of the most recent treatment cycle, the patient should be discontinued from necitumumab treatment.

9.4.1.2.2.1. Necitumumab Dose Modifications

The following are general dose-modification guidelines for toxicity associated with necitumumab. Please see [Section 9.4.1.3](#) for specific information on the management of necitumumab-related hypersensitivity/IRRs, skin reactions, conjunctivitis, and hypomagnesemia.

For patients starting Cycle 1 in Part A and possible Part B of the study at necitumumab 600 mg on Days 1 and 8, one dose reduction is permitted. Patients who cannot tolerate necitumumab 400 mg should discontinue necitumumab; such patients may continue with pembrolizumab as a single agent.

For patients starting Cycle 1 at dose level 800 mg on Days 1 and 8 in Part A and possible Part B and Part C of the study, 2 dose reductions are allowed following reversible CTCAE Grade ≥ 3 AEs that require delay of necitumumab treatment for up to 6 weeks following Day 1 of the most recent treatment cycle, unless DLT criteria are met (Cycle 1 Parts A and C). In this setting, necitumumab may be re-administered at a reduced dose (600 mg) if necessary only if AE is resolved to Grade ≤ 2 . A second dose reduction is permitted for this level of event (Grade ≥ 3). Necitumumab must be discontinued if further dose reduction is required beyond 400 mg on Days 1 and 8 Q3W. The patient may continue to receive pembrolizumab as a single agent.

Necitumumab dose adjustments are allowed both within a cycle and between cycles.

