2	
 Stop the infusion, and resume the infusion when the infusion reaction has resolved to ≤ Grade 1; decrease infusion rate by 50% when the infusion resumes.^a Monitor patient for worsening of condition. If necessary, administer diphenhydramine hydrochloride 50 mg I.V. (or equivalent), acetaminophen 650 mg orally for fever, and oxygen. For all subsequent infusions, premedicate with diphenhydramine hydrochloride 50 mg I.V. (or equivalent); additional premedication may be administered at the investigator's discretion. 	
 Stop the infusion, and resume the infusion when the infusion reaction has resolved to ≤ Grade 1; decrease infusion rate by 50% when the infusion resumes.^a Administer dexamethasone 10 mg I.V. (or equivalent). Monitor patient for worsening of condition. If necessary, administer diphenhydramine hydrochloride 50 mg I.V. (or equivalent), acetaminophen 650 mg orally for fever, and oxygen. For all subsequent infusions, premedicate with diphenhydramine hydrochloride 50 mg I.V. (or equivalent), acetaminophen 650 mg orally (or equivalent), and dexamethasone 10 mg I.V. (or equivalent); additional premedication may be administered at the investigator's discretion.
3-4	
 Stop the infusion and disconnect the infusion tubing from the patient. Administer diphenhydramine hydrochloride 50 mg I.V. (or equivalent), dexamethasone 10 mg I.V. (or equivalent), bronchodilators for bronchospasm, epinephrine, and other medications / treatments as medically indicated. Hospital admission may be indicated. Permanently discontinue necitumumab. 	N/A

Abbreviations: IRRs = infusion-related reactions; I.V. = intravenously; N/A = not applicable.

^a Once the infusion rate has been reduced for a Grade 1 or 2 hypersensitivity/IRRs, it is recommended that the lower infusion rate be utilized for all subsequent infusions. The infusion duration should not exceed 2 hours.

9.4.1.3.1.2. Management of Infusion Reactions for Pembrolizumab

Signs and symptoms usually develop during or shortly after drug infusion and generally resolve completely within 24 hours of completion of infusion.

Table JFCQ.9.5 shows treatment guidelines for patients who experience an infusion reaction associated with administration of pembrolizumab (MK-3475).

Table JFCQ.9.5. Pembrolizumab Infusion-Related Reaction Treatment Guidelines

NCI CTCAE Grade	Treatment	Premedication at Subsequent Dosing

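### After a Grade 3-4 necitumumab infusion reaction in Cycle 1 of Parts A and C, the protocol gives opposite instructions for pembrolizumab; in Part B and later cycles it is ambiguous

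*Protocol*

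**What the plan says.** Protocol 9.4.1.1 is headed for Parts A and C, and it defines a DLT by events in Cycle 1. On severe reactions to either drug it says: "If a Grade 3 or 4 hypersensitivity/IRR to necitumumab or pembrolizumab occurs, this event will not be considered a DLT". It continues that "the patient will not receive any further study therapy and will be replaced in the study by a new patient".

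Protocol 8.1 describes the regimen in these terms: "Study therapy, consisting of necitumumab plus pembrolizumab, will continue until" a stopping reason occurs. Section 4 treats study treatment as the investigational products and adds: "In this study, the IPs are necitumumab (LY3012211; IMC-11F8) and pembrolizumab (MK-3475".

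Table JFCQ.9.4 gives the action for a Grade 3-4 reaction to necitumumab as "Permanently discontinue necitumumab". It does not mention pembrolizumab and is not limited to a part or cycle. The closing paragraph of 9.4.1.2.2.1 says that when necitumumab is altered for its own toxicity, pembrolizumab need not change and its planned schedule should be kept. The same paragraph says that necitumumab should not be delayed for pembrolizumab-related toxicity.

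Table JFCQ.9.5 ends all further trial treatment after a Grade 3-4 reaction to pembrolizumab.

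Protocol 7.3.2 lists, among the circumstances that end study treatment, "A Grade 3 to 4 IRR, and potentially other drug-related AEs, as specified in Section 9.4.1 below".

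SAP 5.4 pre-defines as an important violation only that necitumumab was continued after a Grade 3-4 infusion reaction.

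**The concern.** A site that handles a severe necitumumab reaction from 9.4.1.1 stops both drugs. A site that works from Table JFCQ.9.4 and the end of 9.4.1.2.2.1 stops necitumumab and gives the next pembrolizumab dose on time. Each site can point to protocol text. The event is serious, and the instruction for the second drug should not depend on which page is open.

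The data are affected too. Exposure and treatment-discontinuation counts would mix two practices. Part A patients treated at the recommended dose are pooled with Part B for efficacy (Protocol 12.1, SAP 5.2). Such a patient stays in the ORR denominator after one dose of each drug and a complete baseline scan, even if replaced for the DLT assessment. Whether pembrolizumab went on can then bear on response and PFS.

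The timing makes the overlap relevant. Protocol 9.4.1.3.1.1 says that reactions usually follow the first or second necitumumab administration. On the Day 1 and Day 8 schedule, both fall in Cycle 1.

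**Working it through.** The plan has no figure to reproduce, so the check sets the rules side by side.

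| Place | Reaction to | Scope | Necitumumab | Pembrolizumab |
|---|---|---|---|---|
| Protocol 9.4.1.1 | either drug | Parts A and C, Cycle 1 | stop | stop |
| Table JFCQ.9.4 | necitumumab | no limit stated | stop | not mentioned |
| Protocol 9.4.1.2.2.1, closing paragraph | necitumumab toxicity in general | no limit stated | altered | keep planned schedule |
| Table JFCQ.9.5 | pembrolizumab | no limit stated | stop (all trial treatment) | stop |
| Protocol 9.4.1.2.2.1, closing paragraph | pembrolizumab toxicity in general | no limit stated | do not delay | not addressed |
| Protocol 7.3.2 | drug not named | no limit stated | refers to 9.4.1 | refers to 9.4.1 |

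1. *Necitumumab reaction, Cycle 1, Part A or C.* Rows 1 to 3 all apply. They agree on necitumumab. For pembrolizumab, row 1 says stop and row 3 says keep the schedule. Row 2 does not conflict with row 1 on its own; the conflict arises when row 3 is read with it.
2. *Does a carve-out settle it?* The dose-reduction rules in 9.4.1.2.2.1 step aside when DLT criteria are met. But 9.4.1.1 says that this reaction is not a DLT, so that exception is not triggered.
3. *Necitumumab reaction, Part B or a later cycle.* Row 1 does not reach these patients. The lead-in of 7.3.2 suggests that both drugs stop. Its bullet names no drug and points to 9.4.1, which contains rows 1 to 5. The reference does not give one answer.
4. *Pembrolizumab reaction.* Row 4 ends trial treatment, while row 5 says that necitumumab should not be delayed. Row 4 is the more specific rule, but its precedence is not stated.
5. *SAP 5.4.* The violation item tracks necitumumab only and does not say which drug caused the reaction. Pembrolizumab given after a severe necitumumab reaction is not a pre-defined violation.

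**Size.** The documents give no rate of Grade 3-4 reactions. Take 1% to 3% purely as an illustration.
- Parts A and C together plan 3 + 6 = 9 to 12 + 12 = 24 patients, before replacements. Expected cases: 9 × 0.01 = 0.09 to 24 × 0.03 = 0.72.
- Part B plans 54. Expected cases: 54 × 0.01 = 0.54 to 54 × 0.03 = 1.62.
- One patient's response status moves an ORR based on 54 patients by 1/54 = 1.9 percentage points.

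**The case against.** The best reply is that the specific rule governs. On this view 9.4.1.1 is a special provision for the DLT window, and Table JFCQ.9.4 is general guidance on the reaction itself. A site that stops both drugs also satisfies the table. The text on keeping pembrolizumab is a general statement, partly permissive, in a section that sends infusion reactions to 9.4.1.3. This is a reasonable way to harmonise the text, and it explains why the table alone is not contradictory. But no passage gives 9.4.1.1 precedence, and 9.4.1.3 is silent on pembrolizumab after a necitumumab reaction, so a site looking for an answer is left with the general rule. Table JFCQ.9.5 ends all trial treatment in the parallel case, so the narrower wording of Table JFCQ.9.4 can fairly be read as intended.

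Four stronger readings are tempting and are not supported.
- *That 7.3.2 stops both drugs in every part.* Its bullet names no drug and defers to 9.4.1. Other bullets under the same lead-in stop only the therapy concerned.
- *That the protocol expressly allows pembrolizumab alone after an infusion reaction.* The words "such patients may continue with pembrolizumab as a single agent" concern patients who start at 600 mg and cannot tolerate the 400 mg dose.
- *That one case removes 1 of 6, or 17%, of a dose cohort.* The patient is replaced for the DLT assessment, so the cohort is refilled.
- *That the SAP could not pick the problem up.* SAP 5.4 also includes any other violation that the sponsor's clinical research physician considers important. Detection would rest on that review, but it is not ruled out.

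Follow-up for response and PFS is not lost by rule either, since 10.1.2 continues imaging after treatment stops without progression.

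**Conclusion.** The point holds in a limited form. For a Grade 3-4 necitumumab reaction in Cycle 1 of Parts A and C, the protocol gives opposite instructions for pembrolizumab. In Part B and later cycles the text is ambiguous. The mirror case, a pembrolizumab reaction and its effect on necitumumab, has the same tension.

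This rests on two readings: that study therapy in 9.4.1.1 means both drugs, as 8.1 describes it, and that permanent discontinuation counts as an alteration of necitumumab therapy under 9.4.1.2.2.1. Both are the natural readings, but neither is spelled out.

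The likely number of patients is small, on the assumed rates above, and the DLT count is protected by replacement. The case for acting is the seriousness of the event and consistent exposure and discontinuation data; the primary test is unlikely to move much. This is an internal inconsistency. Nothing here bears on which rule is clinically right.

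**What to change.** The sponsor should reconcile Protocol 7.3.2, 9.4.1.1, the closing paragraph of 9.4.1.2.2.1, and Tables JFCQ.9.4 and JFCQ.9.5. Each should state the same consequence for each drug after a Grade 3-4 reaction to each drug. If the rule is meant to differ by part or cycle, the text should say so and say which section takes precedence.

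The violation item in SAP 5.4 should then follow the reconciled rule: name the drug that caused the reaction and the drug or drugs whose continuation counts as a violation.

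The cost is a wording amendment to the protocol and one line in the SAP. Sample size, visit schedule and analysis methods do not change.
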